#### 20. Safety Evaluations

#### 20.1. Data sets analysed

Participants who received at least one dose of either intervention or placebo will be included in the safety analysis dataset. Results will be presented by the treatment that participants actually received, rather than that to which they were allocated.

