3.6.2 Secondary Outcomes/Endpoints

The secondary outcome measures for the trial (WP-A) are:

For efficacy:

- 1. duration of post-extubation non-invasive respiratory support (all forms of non-invasive ventilation: e.g. nasal CPAP and nasal high low oxygen)
- 2. duration of oxygen supplementation
- 3. number of trial interventions given (both poractant and placebo)
- 4. use of steroids to assist extubation
- 5. duration of stay on PICU and in hospital;
- 6. change over time from baseline of Ventilation Index (VI), Oxygenation Index (OI) and Oxygenation Saturation Index (OSI) while mechanically ventilated, & SpO₂/FiO₂ (SF) ratio.¹
- the score (value) of parent reported outcome measure of respiratory symptoms the "Liverpool Respiratory Symptom Questionnaire" (LRSQ) at 6m (+/-1m) and 12m (+/-1m) (20);

IRAS 220853 Page **20** of **87**

¹ VI and OI are validated physiological measurements reflecting respiratory function (gas exchange) normalised for level of respiratory support provided by MV, but require blood sampling(21). OSI is a validated physiological measurement reflecting respiratory function (gas exchange) normalised for level of respiratory support provided by MV that does not require blood sampling (41). The SF ratio is a non-invasive measure of respiratory function and can be calculated in situations where invasive blood gas monitoring and MV has ceased (22).

8. time from randomisation to meeting study criteria for readiness for Spontaneous Breathing Test

For safety:

- 1. failure to administer the intervention due to any adverse event during preparatory processes (tracheal toilet or BAL)
- 2. failure to complete administration of the intervention due to any adverse event during administration of the intervention (regardless of which arm of allocation)
- 3. incidents of 'air leak' (pneumothorax and pneumomediastinum) occurring before discharge from PICU
- 4. other adverse events and serious adverse events associated with the intervention
- 5. any need to replace the endotracheal tube
- 6. parent reported readmission to hospital (all causes) up to 90 days post randomisation
- 7. death during PICU admission
- 8. all-cause mortality at 90 days post randomisation

IRAS 220853 Page **21** of **87**

Table 1: Objectives and Outcome Measures

Objectives	Outcome Measures	Timepoint(s) of evaluation of this outcome measure (if applicable)

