8.1.1 Immediately prior to administration

A limited physical examination, with minimal handling, must be undertaken in the two hours prior to each administration of the trial intervention (as per Section 8.5.1).

Prior to intervention and in a drug room away from usual staff, the study respiratory physiotherapist, research nurse or other delegated, unblinded staff member will:

- Draw up a dose of poractant alfa or an equal volume of air as placebo according to the random allocation into a syringe
- Ensure a second person is present to witness this process and check the dose volume
- Cover the syringe with an opaque paper shield to maintain blinding of other staff and parents
- Take the syringe to the bedside, along with syringes of sterile 0.9% sodium chloride for tracheal toilet and the BAL sampling set.

Infants in both the treatment and placebo arms of the trial will have 0.9% sodium chloride "normal saline" tracheal toilet and 0.9% sodium chloride BAL immediately prior to administration of the intervention. Both can cause immediate transient desaturation, need for increased sedation but also and more often rapid improvement in gas exchange when obstructing secretions are removed. Tracheal toilet and BAL can also lead to creamy white secretions appearing in the endotracheal tube, and this will be observed in both treatment and placebo groups.

Staff should remind parents, if present, of the purpose of the imminent study procedure and give them the opportunity to remain or leave as they choose. The usual care nurse will remain to care for the participant and assist as required.

Tracheal toilet is usually required for babies with bronchiolitis and will be done as recommended in the SPC before administration of poractant alfa. BAL sampling with 0.9% sodium chloride (2x1mL/kg) will be done if scheduled (section 8.2). Both tracheal toilet and BAL sampling is done by catheter access to the trachea; either via the endotracheal suction port without disconnecting the

IRAS 220853 Page **34** of **87**

infant from the ventilator or by disconnecting the infant from the ventilator and performing hand bagging while a side-port with one-way valve are utilised for the toilet and BAL.

The use of muscle relaxant prior to tracheal toilet, BAL and or administration of the intervention is at clinical discretion.

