8.6.2 Special Assays or Procedures

8.6.2.1 Collection & processing of BAL fluid

BAL sampling with 0.9% sodium chloride (2x1mL/kg) will be done for all participants immediately prior to intervention, at 24hrs post intervention and repeated daily while the infant remains on MV (see Table 2).

Both tracheal toilet and BAL sampling is done by catheter access to the trachea via the endotracheal suction port without disconnecting the infant from the ventilator or by disconnecting the infant from the ventilator and performing hand bagging while accessing the trachea via a side-port with one-way valve.

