10.7 Time Period for Safety Reporting

Investigators and delegated members of the local research teams will report to CTRC on the appropriate CRFs (see section 10.8):

- all adverse events from randomisation until 24 hours after their final intervention (whether poractant alfa or placebo);
- all adverse reactions from randomisation until 90 days post-randomisation or hospital discharge (whichever is sooner).

Following these periods, site staff are not required to report any non-serious events, however any serious events (SAEs/SARs/SUSARs) which they become aware of must be reported to CTRC.

[figure not shown]
Upon becoming aware of a serious adverse event (SAE/SAR/SUSAR), the Investigator or other delegated member of the team **must** report this to the CTRC **within 24 hours**.

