# 17.5.1.1. Derivation

The details of failure to administer intervention can be found on the Treatment CRF.

A failure to administer the intervention due to any adverse event during preparatory processes (tracheal toilet or BAL) is indicated where the variable TRTINSTC=" Intervention not done" and the variable TRTISTRC = "F - Adverse Event during preparatory process".

A failure to complete administration of the intervention due to any adverse event during administration of the intervention is indicated where the variable TRTINSTC=" Intervention not completed" and TRTISTRC is one of ("E - Adverse Event", "G - Serious Adverse Event").

# Form prepared: 16/04/2024 v2.0 for BESS Page 23 of 30

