#### 20.2. Presentation of the data

All AEs reported by the clinical investigator will be presented, with separate tables for serious and non-serious events. Both the number of events and the number of patients experiencing each event will be provided. A third table will be presented grouping non-serious AEs by severity; participants will be counted in the most severe category experienced if they experienced more than one. Similarly, a fourth table will be presented grouping non-serious ARs by causality (where the relationship to intervention is recorded as possibly, probably or almost certainly) and participants will be counted in the highest relationship category experienced if they experienced more than one.

The above tables for serious and non-serious events will be repeated but will be further grouped by whether or not the patient received muscle relaxant prior to the administration of the intervention. Serious adverse reactions will be presented as line listings, detailing the description, seriousness, severity, expectedness, relationship to intervention and outcome.

Relationship to study drug will be assessed first assuming the participant is in the intervention arm, then assuming they are in the control arm, so as to avoid unnecessary unblinding. However, for the classification of causality only the relationship to the intervention received will be reported.

For all AE descriptions, MedDRA classifications will be used. Events will be reported using the preferred term, categorised by system organ class. Results will be presented descriptively; no formal statistical testing will be undertaken for interim reports.

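### The dosed-only safety set leaves adverse events in infants never dosed after a failed preparation outside the adverse-event tables, and SAP 20.1 and 20.2 disagree on this

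*SAP*

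**What the plan says.** SAP 20.1 defines the safety dataset: "Participants who received at least one dose of either intervention or placebo will be included in the safety analysis dataset". The next sentence sets the grouping: "Results will be presented by the treatment that participants actually received, rather than that to which they were allocated". SAP 20.2 then describes the content of the tables: "All AEs reported by the clinical investigator will be presented, with separate tables for serious and non-serious events". Neither section mentions an infant who was randomised and prepared but never dosed.

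The protocol places trial procedures before the first dose. Section 8.6.2.1 says: "BAL sampling with 0.9% sodium chloride (2x1mL/kg) will be done for all participants immediately prior to intervention". Section 8.1.1 applies tracheal toilet and lavage to both arms and says of them: "Both can cause immediate transient desaturation, need for increased sedation".

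Collection of adverse events starts before any dose. Protocol 10.7 requires sites to report "all adverse events from randomisation until 24 hours after their final intervention (whether poractant alfa or placebo").

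The protocol also foresees an abandoned preparation. Section 3.6.2 lists as its first safety outcome "failure to administer the intervention due to any adverse event during preparatory processes (tracheal toilet or BAL"). SAP 17.5.1.1 identifies it on the Treatment CRF by an intervention recorded as not done, with reason "F - Adverse Event during preparatory process".

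**The concern.** The trial's own procedures begin with tracheal toilet and lavage, and the protocol names acute effects of both. An infant who has such an event at the first intervention, and is never dosed, has been exposed to a trial procedure and has a reported event. The rule in 20.1 nevertheless excludes that infant, and in this scenario the exclusion is a consequence of the event itself.

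What is at stake is the description of procedure-related harm. A reader of the final report would look to the adverse-event tables for what happened, how severe it was, whether it was serious and whether it was judged related. For these infants the tables would be silent, although the data had been collected. The two SAP sections also give opposite answers. SAP 21 has an independent statistician program the safety analysis from the SAP without sharing code, so two competent programmers could reach different tables.

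**Working it through.** No figure in the plan needs reproducing on this point. The check follows one hypothetical infant through the rules.

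**The infant.** Randomised; tracheal toilet or lavage started for the first intervention; an adverse event occurs; the intervention is abandoned; no dose is given at the later time points.

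1. *Is the event collected?* Yes. Protocol 10.7 starts at randomisation.
2. *Is the infant in the safety dataset?* No. SAP 20.1 requires at least one dose of active or placebo.
3. *Which column would the infant enter?* None. The grouping is by treatment received, and nothing was received. The 20.2 rule that reports causality only for the intervention received is undefined here for the same reason.
4. *Does another sentence bring the event back?* Read literally, the opening of 20.2 does, because it covers all reported events. It does not say that it overrides 20.1 or where the event would be shown. The two sections conflict and the SAP does not say which governs.
5. *Is the infant counted elsewhere?* Yes. SAP 17.5 applies intention to treat to Safety Outcome 1, so the failed administration is counted by allocated arm.
6. *Does that count carry the same information?* No. SAP 17.5.1.2 gives the number of failures, the number of patients and a two-way table. The MedDRA term, severity, seriousness and causality are specified only in 20.2.

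**Possible size.** The documents give no rate for the full sequence (event during preparation, first intervention abandoned, no later dose). The rates below are assumptions. The planned sample size, 284, is from Protocol 11.3. The expected number is 284 × q, and the chance of at least one such infant is 1 − (1 − q)^284.

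| Assumed rate q | 284 × q | Chance of at least one |
|---|---|---|
| 0.5% | 1.42 | 76% |
| 1% | 2.84 | 94% |
| 2% | 5.68 | 99.7% |
| 3% | 8.52 | above 99.9% |

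The assumed range therefore covers about 1 to 9 infants. Even at its lower end, the case is more likely than not to arise once.

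**The case against.** The strongest reply is that little is lost.

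- **The scenario is reported elsewhere.** Failure to administer because of an event in preparation is a prespecified outcome under intention to treat. So are air leak, tube replacement, death in PICU and 90-day mortality. Reasons for missed doses appear in the compliance and disposition summaries, and serious events still go to the coordinating centre within 24 hours. This stands. It rules out a reading that such events vanish from all safety reporting; the gap is confined to the adverse-event tables.
- **A dosed-only set is conventional.** It also fits Protocol 10.1, which defines an adverse event in a subject given a medicinal product. This stands as a reason to keep that set for comparing surfactant with air. It does not settle what happens to events that 10.7 requires to be collected before any dose.
- **The comparison of arms is hardly touched.** Tracheal toilet and lavage are done in both arms before any product is given. This stands. A reader might infer bias between arms, but the documents do not support that.
- **SAP 20.2 already promises every event.** This stands only in part: it shows a conflict with 20.1 and does not resolve it.

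Three further inferences should be resisted. First, not every infant with a lavage-related event is dropped: one who is dosed then or later is in the dataset. Nor is every never-dosed infant there because of an event, since parental withdrawal or transfer can also prevent dosing. Second, Protocol 3.4.2 cites 7 of 27 children with transient desaturation, but at a larger lavage (5 × 1 mL/kg, against 2 × 1 mL/kg here). That counts desaturation, not abandoned procedures, so it gives no rate for this problem. Third, one might suspect that the coding in 17.5.1.1 misses serious preparatory events. Reason F is not limited to non-serious events, and how sites would code depends on a CRF that is not shown.

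**Conclusion.** The point holds in a narrow form. As written, SAP 20.1 leaves an infant who is never dosed after an adverse event in preparation outside the adverse-event tables, and this conflicts with SAP 20.2. The failed administration is counted in Safety Outcome 1; the description and grading of the event are not.

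The number affected is unknown and probably small: about 1 to 9 infants if the assumed 0.5% to 3% of 284 is near the truth. The effect is mainly understated harm from the trial procedure in both arms together.

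The conclusion assumes that preparation still includes tracheal toilet and lavage under the protocol version in force. The protocol supplied is version 2.0 and the SAP refers to later versions, but SAP 17.5.1 still names both procedures. A correction is worthwhile because the data are already collected and the rule can be settled in wording.

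**What to change.** Keep the at-least-one-dose, as-treated set in SAP 20.1 for the product comparison. Add to 20.1 that adverse events and serious adverse events from randomisation are also tabulated for infants in whom a trial procedure (tracheal toilet, lavage or instillation) was started but no dose was given. Show term, severity, seriousness and causality, as a separate row or table under the allocated arm.

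In 20.2, say that the commitment to present all events is met by the two displays together. Say also which causality assessment is shown where no intervention was received. The dataset-definitions template described in SAP 15, which must be approved before the randomisation codes are released, is a natural place to record the rule.

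The cost is SAP wording and one additional small table. No new data are needed.

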#### 20.2. Presentation of the data

All AEs reported by the clinical investigator will be presented, with separate tables for serious and non-serious events. Both the number of events and the number of patients experiencing each event will be provided. A third table will be presented grouping non-serious AEs by severity; participants will be counted in the most severe category experienced if they experienced more than one. Similarly, a fourth table will be presented grouping non-serious ARs by causality (where the relationship to intervention is recorded as possibly, probably or almost certainly) and participants will be counted in the highest relationship category experienced if they experienced more than one.

The above tables for serious and non-serious events will be repeated but will be further grouped by whether or not the patient received muscle relaxant prior to the administration of the intervention. Serious adverse reactions will be presented as line listings, detailing the description, seriousness, severity, expectedness, relationship to intervention and outcome.

Relationship to study drug will be assessed first assuming the participant is in the intervention arm, then assuming they are in the control arm, so as to avoid unnecessary unblinding. However, for the classification of causality only the relationship to the intervention received will be reported.

For all AE descriptions, MedDRA classifications will be used. Events will be reported using the preferred term, categorised by system organ class. Results will be presented descriptively; no formal statistical testing will be undertaken for interim reports.

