3.4.2 Potential Risks

Administration of poractant alfa (porcine derived surfactant, Curosurf®) in infants with bronchiolitis is well tolerated and considered safe(3). Transient minor adverse reactions associated with administration of poractant alfa for the treatment of neonatal Respiratory Distress Syndrome (RDS) include bradycardia, hypotension, endotracheal tube blockage, and oxygen desaturation. The risk of such events is minimised by tracheal toilet prior to administration of poractant alfa, as recommended in the Summary of Product Characteristics.

Small volume (2x1mL/kg) non-bronchoscopic bronchoalveolar lavage (BAL) procedure on PICU is safe and well tolerated procedure(7). In a published audit of 27 children on PICU who underwent multiple small volume BAL installations (5x1mL/kg) as part of a single routine diagnostic procedure, 7 experienced transient oxygen desaturation requiring temporary increased FiO₂. We will limit BAL sampling to a 2x1mL/kg instillation at each scheduled assessment.

Small volume (1.25mL (range 1.0 to 1.3mL)) blood sampling will be done on infants ventilated at Liverpool and Southampton PICUs and scheduled to coincide with routine blood sampling. Existing vascular access will be used when available. There is no risk of anaemia associated with this limited volume of blood sampling. The sample will be taken from an arterial line if present. If not by standard venesection.

Capillary blood gas sampling (100microliters) or arterial blood gas sampling for subject monitoring will use data from routine blood gas sampling when either is collected within a 2-hour window of a research-scheduled sample. As this is part of standard care no additional risks are expected.

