8.5 Procedures for Assessing Safety

Safety will be assessed by:

- The Principal Investigator (PI) or delegated research staff actively monitoring and reporting all adverse events from randomisation until 24 hours after the participant's last administration of poractant alfa (see section 10 for adverse event reporting).
- Limited physical examination that includes the recording of vital signs before and after each study intervention
- Routinely collected patient care data downloaded from the PICANet audit on a regular basis by each site and transferred to the CTRC
- Mortality and readmission data collected by each site at 90 days post randomisation

Participants will be actively monitored and any adverse events identified must be reported to the CTRC, whether identified from trial assessments or standard care (e.g. identified during standard daily examinations). Non-related events will be reported from randomisation to 24 hours after the participant's last administration of poractant alfa or placebo for. Adverse events occurring after this time point until 90 days post randomisation / discharge home / death will be reported if felt to be related to the intervention. Any serious events or reactions (SAEs/SARs) should be reported to CTRC regardless of the timeframe.

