8.5.1 Procedure for Limited Physical Examination in BESS

Participants in BESS are unwell and may be haemodynamically unstable. Handling of the participants, including full physical examination, is minimised in standard care, as per current NICE guidance (42).

All participants must have a physical examination before and after each administration of the trial intervention. This is a limited physical examination to minimise any disturbance to the infant participant.

Examinations must be carried out any time in the period 2 hours prior to each administration, and the interval of time between 1 hour and 2 hours post each administration. The post administration examination is deliberately delayed by at least one hour after administration to allow stabilisation of the participants' vital signs and avoid prolonging the handling associated with administration. The limited examination must include the following:

- Temperature
- Heart rate
- Blood pressure
- Respiratory rate
- Oxygen saturations (peripheral)

To minimise handling, if a participant has had a full physical examination as part of standard care at any time in the period 2 hours prior to the administration and the vital signs data have been collected, then this examination should be counted as their BESS physical examination and the vital sign data used.

The physical examination vital sign data must be recorded in the patient notes and transcribed onto the relevant BESS CRF.

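### Protocol 8.5 makes pre- and post-dose vital signs a safety assessment, but the SAP has no output for heart rate, blood pressure or the per-dose change in any examination sign

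*SAP*

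**What the plan says.** **Protocol.** Section 3.4.2 gives the transient reactions known from use of the product in neonatal respiratory distress: "bradycardia, hypotension, endotracheal tube blockage, and oxygen desaturation". Section 8.5 lists four ways in which safety will be assessed, one of them being "Limited physical examination that includes the recording of vital signs before and after each study intervention". Section 8.5.1 adds that "All participants must have a physical examination before and after each administration of the trial intervention". It fixes the content as five signs: temperature, heart rate, blood pressure, respiratory rate and peripheral saturation. The first reading falls in the two hours before a dose, the second between one and two hours after it. On timing it says "The post administration examination is deliberately delayed by at least one hour after administration", so that the signs can settle and handling is not prolonged. On data it says "The physical examination vital sign data must be recorded in the patient notes and transcribed onto the relevant BESS CRF".

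**SAP.** Section 17.5 defines six safety outcomes: failure to give or complete a dose because of an adverse event, air leak, parent-reported readmission, tube replacement, death in PICU, and mortality to day 90. Section 20.1 defines a safety set of infants who received at least one dose, grouped by treatment received. Section 20.2 states "All AEs reported by the clinical investigator will be presented, with separate tables for serious and non-serious events", then adds tables by severity, causality and muscle-relaxant use, coded in MedDRA. Section 17.4.4 analyses VI, OI, OSI and the SF ratio as efficacy outcomes.

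**The concern.** Safety is a stated aim and a secondary objective, and Protocol 9.1 describes this as the first large randomised study of any surfactant in this disease. The protocol obtains a measured reading of heart rate and blood pressure on either side of every dose, in both arms, and calls this a safety assessment. The SAP then gives those readings no derivation, table or comparison.

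If the SAP is followed as written, a shift in heart rate or blood pressure is visible only if someone at the bedside declares an adverse event, or stops a dose and codes an adverse event as the reason. That route involves judgement. Under Protocol 10.2.1 an abnormal examination counts when it needs further investigation or clinical intervention, and 10.2.2 leaves out recognised features of bronchiolitis. Protocol 7.4 expects some caregivers to infer the allocation and regards the usual care nurse as likely to become unblinded. Readings taken in both arms at fixed times depend less on that judgement, and they are already collected.

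**Working it through.** The plan states no figure on this point, so the check traces each examination sign through the SAP, compares the timing, and then counts what is left without an output.

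**1. Where each sign appears in the SAP**

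| Sign (Protocol 8.5.1) | Use in the SAP | Pre/post-dose change reported? |
|---|---|---|
| Temperature | none | no |
| Heart rate | none | no |
| Blood pressure | none | no |
| Respiratory rate | one component of VI (17.4.4.1) | no |
| SpO₂ | SF ratio and OSI (17.4.4) | no |

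Heart rate and blood pressure have no direct output. Their only routes are the adverse event tables in 20.2 and the administration-failure outcome in 17.5.1, which is read from Treatment CRF reason codes that name an adverse event.

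**2. Timing of the SpO₂ indices against the examination**

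- Examination (Protocol 8.3, Table 2): before each dose, and 1–2 hours after each dose.
- SF and OSI (SAP 17.4.4): immediately before the intervention, then 6, 12, 24, 36 and 48 hours, and onward; SF also continues after ventilation.

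Table 2 schedules no blood gas or data-collection entry in the 1–2 hour post-dose columns. The 12- and 24-hour index readings are themselves pre-dose readings for doses 2 and 3. Routine readings, which Protocol 8.4.2 wants transcribed, may happen to fall near an examination, but nothing links them to it. SF divides SpO₂ by FiO₂, and OSI combines SpO₂ with FiO₂ and airway pressure. Neither is a per-dose saturation change.

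**3. Volume of readings with no planned output**

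Inputs: 284 participants (Protocol 11.3), up to 3 doses, 2 examinations per dose.

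- Examinations: 284 × 3 × 2 = 1,704
- Heart rate and blood pressure readings: 1,704 × 2 = 3,408
- Adding examination SpO₂: 1,704 × 3 = 5,112
- All five signs: 1,704 × 5 = 8,520

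These are upper bounds, because not every infant receives three doses.

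**4. What a dose-1 comparison could deliver**

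With 142 infants per arm (Protocol 11.3), all dosed and examined, the standard error of the between-arm difference in mean change is √(2/142) = 0.119 in units of the SD of the change. The 95% half-width is 1.96 × 0.119 = 0.23 SD. The documents give no SD, so this cannot be put into beats per minute or mmHg.

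**The case against.** The case on the other side has four parts, and much of it stands.

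- **Saturation is analysed.** A reader might infer that the SAP ignores all three haemodynamic and saturation risks named in Protocol 3.4.2. It does not. SpO₂ is modelled by arm through the SF ratio (repeated measures) and OSI (joint model). Only the per-dose change is missing.
- **The adverse event route is wider than one rule.** Protocol 10.1 defines an adverse event broadly, 10.2.1 gives several ways to qualify, and events are actively monitored from randomisation to 24 hours after the last dose, which covers instillation itself. MedDRA preferred-term tables would show bradycardia, hypotension and desaturation separately. Administration failure and tube replacement are also compared by arm. So these harms are not unmonitored. A reader might go further and argue, from power calculations, that adverse event counts would miss most of a real shift. That would need an assumed effect size and an assumed numerical cut-off for declaring an event. The documents give neither, and the adverse event route is not a cut-off applied to the 1–2 hour reading.
- **The reading is late by design.** The post-dose examination is "deliberately delayed by at least one hour after administration to allow stabilisation", while 3.4.2 calls the reactions transient. A null result at 1–2 hours could reassure falsely. This limits what a table can show. It does not explain why a listed safety assessment has no output.
- **Motive.** A reader might infer that the examinations exist because of the risks in 3.4.2. The protocol does not say so. That section links tracheal toilet to reducing those risks, and the amendment log records that the examinations were added without giving a reason.

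There is also a version gap. The supplied protocol is v2.0. The SAP states compliance with v3.0, its change control lists v6.0, and its section 17.4.2.1 cites a protocol section 8.1.4.1 that v2.0 does not contain. Later wording on vital signs could not be checked.

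**Conclusion.** The point holds as a reporting gap. One of the four safety assessments listed in Protocol 8.5 has no planned output, amounting to at most 1,704 examinations. The gap is complete for heart rate, blood pressure and temperature. For SpO₂ and respiratory rate it is confined to the change across a dose. It does not touch the primary analysis, and it does not show that any harm would go undetected, since adverse events are monitored through dosing and tabulated.

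The documents do not support reading the 1–2 hour values as a measure of the transient reactions. They can show persistent change only. The conclusion assumes that the examinations in protocol v2.0 were still required, and still on the CRF, under the version in force.

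**What to change.** Add to SAP 20.2, on the safety set in 20.1:

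- For each of the five examination signs, a table by arm and by dose of the pre-dose value, post-dose value and change, with the number of infants contributing and the number missing.
- At dose 1, the between-arm difference in mean change with a 95% CI. SAP section 12 plans no multiplicity adjustment, so these five intervals should be presented as descriptive.
- Doses 2 and 3 summarised descriptively only. Only infants still intubated receive them, so the arms at those doses are no longer the groups formed by randomisation.
- A footnote that the post-dose reading is taken at 1–2 hours, after intended stabilisation, so it reflects persistent change and does not rule out transient bradycardia, hypotension or desaturation at instillation.

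Before adding this, confirm against the current protocol that the examinations and their CRF fields stand as described, and state which blood pressure measure the CRF holds. If the sponsor prefers not to report these data, the SAP should say so and give the reason.

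The cost is SAP wording and a few tables. No new data collection or procedure is needed.
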